### **2.13.2. Secondary Endpoints**

The secondary endpoints measure:

- Time to maximum PVR decrease;
- Repeated measures ANOVA (RM-ANOVA) for change in PVR calculated from the start of inhalation and at times 15, 30, 45 and 60 minutes post end of nebulization.
- Change in mean pulmonary artery pressure, transpulmonary gradient and cardiac output (CO)/cardiac index (CI),
- Change in systemic blood pressure,
- Change in SVR, RV systolic (dP/dtmax/IP, PWRmax/EDV, RV EF, TAPSE), RV diastolic function (dP/dtmin, Tau),
- Changes in pulmonary vascular impedance / Wave Intensity,
- Change in plasma nitrite concentrations, cGMP, and platelet mitochondrial activity in mixed venous blood at specified time-points,

Change in pulmonary artery occlusion (capillary) pullback nitrite and plasma cGMP at baseline compared with both nitrite doses.

## **2.14. SUBJECT WITHDRAWAL**

A subject may voluntarily discontinue participation in this study at any time. The investigator may also, at his or her discretion, discontinue a subject from this study at any time. Every effort should be made by the investigator to keep the subject in the study.

Subjects may be withdrawn from the study prior to completion if any of the following criteria are observed:

- Intercurrent illness or an unexpected fatal or life-threatening adverse event, which requires discontinuation of study treatment
- Pregnancy
- Subject reached protocol-defined stopping criteria
- Request by the subject to withdraw from the study
- Protocol violations
- Persistent non-compliance
- Lost to follow-up
- Investigator discretion
- Study closed/terminated

### **2.14.1. Dropouts and withdrawals**

To be considered complete, a subject must complete all study visits as specified in the protocol without violations of the protocol so significant as to obscure the response to study treatment.

Subjects who fail to complete all study required visits will not be considered complete and may not enroll at a later date and will not be replaced. A record will be kept of all subjects who fail to complete all study visits and their primary reasons for discontinuation.

In the event of subject withdrawal, subjects will be encouraged to continue all follow-up visits for safety monitoring or to continue follow up as directed by their personal primary physicians, unless the subject withdraws consent at any time (without having to justify the decision). All available data from subjects who discontinued during the study, for whatever reason, will be included in the safety analysis.

## 2.15 STATISTICAL ANALYSIS

### 2.15.1 Sample Size and Power

Limited data are available on expected vasodilatory responses to nitrite in patients with Group I PAH or Group III PH. We reviewed data from studies examining the PVR response to inhaled NO, fasudil, iloprost, and treprostinil, which reported percent decreases in PVR after therapy ranging from 5-25%. Assuming a distribution of PVR among PAH patients similar to that reported by Voswinckel, et al (911 +/- 102 dyn·sec·cm^-5), we estimate using the paired t-test that we will need 14 participants to achieve 80% power to detect a statistically significant 10% decrease in PVR at a significance level of 0.05. At a projected enrollment of approximately 20 patients with group I PAH for our primary outcome measure, we anticipate more than sufficient power to detect significant acute vasodilatory effects of nitrite.

### 2.15.2 Statistical Analysis

#### General Approach

The primary efficacy outcome variable is pulmonary vascular resistance (PVR), measured by right heart catheterization. T-test will be performed to determine difference of mean values for outcome variables at baseline and highest tolerated nitrite. The secondary endpoints will be analyzed with repeated measures ANOVA (RM-ANOVA) to compare the overall cardiopulmonary hemodynamic effects and the PK endpoints (eg: AUC) for all doses of nitrite.

#### Safety Analysis

Adverse events (AEs) will be grouped by body system. AEs occurring pre-treatment, during active treatment and post-treatment will be summarized separately. The number and percentage of subject experiencing at least one AE of any type, AEs within each body system and AEs within each preferred term will be tabulated and listed. Separate summaries will be provided for all AEs, AEs by maximum severity, drug related AEs, severe adverse events (SAEs), and for AEs leading to withdrawal.

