## **2.2 STUDY TREATMENT**

Following initial standard clinical measurements for right heart catheterization, 40 ppm inhaled NO gas will be administered for approximately 5-15 minutes through a facemask, continuously monitoring subject vasoreactivity. This is considered part of the clinical right heart catheterization procedure for pulmonary hypertension. Repeat hemodynamic measurements will be performed upon completion of inhaled NO. Pre-dose baseline PK and methemoglobin levels may be collected. The inhaled nitrite will be delivered per protocol below.

Following completion of all baseline assessments, each subject will receive a starting dose of inhaled nitrite, with one subsequent planned dose escalation of inhaled nitrite, based on safety and tolerability. Subjects will be monitored carefully during and after the study treatment.

The study will be conducted at UPMC Presbyterian Hospital, 3rd FL Catheterization Laboratory. Baseline vasoreactivity will be recorded after Inhaled NO at 40 ppm for approximately 5-15 minutes. Subjects will receive a starting dose of AIR001 (45 mg), with one subsequent planned dose escalation to 90 mg based upon safety and tolerability. The dose of AIR001 will be delivered by an electronic nebulizer system that is portable, highly efficient utilizing continuously vibrating mesh aerosol generation technology that allows a high percentage respirable dose delivery, minimal loss of drug to the environment between inhalations, and a reproducible droplet size distribution for optimal delivery of drugs to the distal pulmonary tree.

During, and at approximate timelines of 15, 30, 45 and 60 minutes post-inhalation for each dose, right heart/pulmonary artery hemodynamics will be measured as well as noninvasive systemic

blood pressure monitoring. Subjects will be monitored closely during the study. Dose limiting toxicity (DLT) is defined in Table 1.

A dose level will also be considered intolerable if, in the judgment of the Investigator, the type, frequency, or severity of AEs becomes unacceptable. If an intolerable dose is identified, no further doses at that or higher doses will be administered.

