##### **5.5.5.1. Adverse event definitions**

Adverse event. Any untoward medical occurrence in a clinical study; regardless of the causal relationship of the event with the investigational drug or study treatment(s).

Associated with the use of the investigational drug or study treatment(s). There is a reasonable possibility that the adverse event may have been caused by the investigational drug or study treatment(s).

Disability. A substantial disruption of a person's ability to conduct normal life functions.

Life-threatening adverse event. Any adverse event that places the patient or subject, in the view of the investigator, at immediate risk of death from the event as it occurred (i.e., does not include an adverse event that, had it actually occurred in a more severe form, might have caused death).

Serious adverse event. Any adverse event occurring at any dose that results in any of the following outcomes: death, a life-threatening adverse event, inpatient hospitalization or prolongation of existing hospitalization, a persistent or significant disability/incapacity, or a congenital anomaly/birth defect.

- Hospitalization shall include any initial admission (even if less than 24 hours) to a healthcare facility as a result of a precipitating clinical adverse event; to include transfer within the hospital to an intensive care unit. Hospitalization or prolongation of hospitalization in the absence of a precipitating, clinical adverse event (e.g., for a preexisting condition not associated with a new adverse event or with a worsening of the preexisting condition; admission for a protocol-specified procedure) is not, in itself, a serious adverse event.

Unexpected adverse event. Any adverse event, the frequency, specificity or severity of which is not consistent with the risk information described in the clinical protocol(s) or elsewhere in the current IND application, as amended.

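### The safety plan specifies no adverse event or dose-limiting toxicity frequency by dose (45 mg versus 90 mg), and it expands SAE as severe where the protocol defines serious

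*Combined protocol and SAP*

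**What the plan says.** The combined protocol and SAP gives one paragraph to safety, in section 2.15.2 (Safety Analysis). Its time axis has three periods: "AEs occurring pre-treatment, during active treatment and post-treatment will be summarized separately". Within these, "AEs within each body system and AEs within each preferred term will be tabulated and listed", and separate summaries are promised for "all AEs, AEs by maximum severity, drug related AEs, severe adverse events (SAEs), and for AEs leading to withdrawal". Dose does not appear, and neither does DLT.

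The dosing is sequential within subject. Section 2.2 (Study Treatment): "Subjects will receive a starting dose of AIR001 (45 mg), with one subsequent planned dose escalation to 90 mg based upon safety and tolerability". The Synopsis puts the second dose about 60 minutes after the first. The same section 2.2 defines DLTs through Table 1, with Moderate and Severe columns, and adds: "A dose level will also be considered intolerable if, in the judgment of the Investigator, the type, frequency, or severity of AEs becomes unacceptable".

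On terminology, section 5.5.5.1 defines by outcome: "Serious adverse event. Any adverse event occurring at any dose that results in any of the following outcomes: death, a life-threatening adverse event". The stopping rules in sections 2.6 and 5.5.2 also use the word serious.

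**The concern.** Tolerability of the escalation is part of what the trial sets out to show. The Synopsis hypothesises safe delivery with few dose-limiting symptoms in patients on background therapy. Section 1.3.5 calls the interaction with oral PAH therapy unknown and gives that as the reason for escalating. Section 5.1 reports that in the first-in-man study heart rate rose with dose and blood pressure fell at the highest dose. A reader of the final report will want to know how often events arose after 45 mg and how often after 90 mg. The planned tables, followed as written, do not answer that.

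The SAE wording is a smaller, separate matter in the same paragraph. A summary of severe events largely repeats the maximum-severity summary already listed, and the serious events defined in section 5.5.5.1 would then have none.

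**Working it through.** The plan states no safety rate or precision target, so there is no figure to reproduce. The check has two parts.

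**Text check**

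| Item | Where | By dose? |
|---|---|---|
| AE tables | 2.15.2, Safety Analysis | No: three periods, then body system, preferred term, severity, relatedness, withdrawal |
| DLT definition | 2.2, Table 1 | Defined; no count or rate planned anywhere |
| Dose-level tolerability | 2.2 | Judged by type, frequency or severity of AEs at a dose level |
| AE assessment | 2.10.2 and 2.11 | Yes: listed under Dose 1 and again under Dose 2 |
| Systemic blood pressure | 2.13.2 and 2.15.2, General Approach | Yes: repeated measures ANOVA over all doses, as a mean change |

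AEs are thus assessed at each dose and dose levels are judged on AE frequency, but the planned tables drop the dose.

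**What the pooled count can and cannot identify**

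The documents give no event rates, so the counts here are assumed. Take 50 subjects (section 2.2.1). Suppose each subject with an event after 45 mg does not go on to 90 mg and all others do. With event probabilities p45 and p90, the proportion with an event during active treatment is p45 + (1 − p45) × p90. Three cases give the same total:

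- 0/50 at 45 mg and 6/50 at 90 mg: 0 + 1 × 0.12 = 0.12.
- 3/50 (6%) at 45 mg and 3/47 (6.4%) at 90 mg: 0.06 + 0.94 × 0.0638 = 0.12.
- 6/50 (12%) at 45 mg and 0/44 at 90 mg: 0.12 + 0.88 × 0 = 0.12.

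A pooled line of 6/50 = 12% is the same in all three.

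**Denominator**

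A second illustration, again with assumed counts: 20 subjects dosed, 15 of whom receive 90 mg, and four hypotension events, all after 90 mg. Exact (Clopper-Pearson) 95% intervals:

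- Over all 20: 4/20 = 20.0% (5.7 to 43.7%).
- At 45 mg: 0/20 (0 to 16.8%).
- At 90 mg, over those who received it: 4/15 = 26.7% (7.8 to 55.1%).

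Over all treated subjects, the 90 mg rate is understated by the factor 15/20. Some non-escalation is foreseeable: Table 1, footnotes 1 and 5, and section 2.6 stop dosing for individual subjects, and section 2.14.1 keeps the available data of those who discontinue in the safety analysis.

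**Precision to expect**

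With 50 subjects at a dose, 0 events gives 0 to 7.1% and 5 events gives 3.3 to 21.8%. With 0 events in a diagnostic group of 20 the upper limit is 16.8%, and in the group of 10 it is 30.8%.

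**Severe versus serious**

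Section 2.15.2 has "severe adverse events (SAEs), and for AEs leading to withdrawal"; section 5.5.5.1 has "Serious adverse event. Any adverse event occurring at any dose that results in any of the following outcomes". The two are not interchangeable. Table 1 classes methemoglobin of 7% or more as Severe without requiring any of the outcomes that make an event serious.

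**The case against.** The best case for the plan is that it is silent on dose, not opposed to it. AEs will also be listed, assessments are made at each dose, and nothing prevents a by-dose table later. Several stronger statements that a reader might infer are not supported:

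- *That the trial would report no dose-related safety information.* Systemic blood pressure, the measure named in Aim 3, is a secondary endpoint analysed over all doses. This stands, but a mean change is not an event rate.
- *That DLTs are left out of the analysis.* Under section 5.5.5.2 (Abnormal test findings), a finding with symptoms, needing intervention or changing dosing counts as an AE. With bronchospasm, dyspnea and cough, most Table 1 events would enter the AE tables. They would enter without a DLT label and without a dose.
- *That the plan fixes one pooled denominator.* It promises numbers and percentages of subjects and names no denominator. It does not define active treatment either; that both doses fall in it follows from the dosing sequence.
- *That the trial hypothesises a difference between 45 mg and 90 mg.* The hypotheses concern safety in patients on background therapy. The case for a by-dose summary rests on the dose-level rule in section 2.2 and the hypothesis about dose-limiting symptoms.
- *That AE onset time is already recorded.* No section says so. Only an assessment at each dose is documented.

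The SAE expansion is probably a slip, since the rest of the protocol uses serious and section 5.5.2 separately requires a written summary of serious, unexpected, related events. It still needs correcting, because tables are programmed from this paragraph.

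**Conclusion.** The point holds in this form: as written, the plan yields no AE or DLT frequency by dose, and its SAE wording conflicts with the protocol's own definition. It should be changed, because section 2.2 calls for AE frequency at a dose level and the assessments are already scheduled by dose. The primary endpoint, PVR, is not affected.

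The size cannot be given as a bias in a stated figure. What can be shown is non-identification: a pooled 12% is compatible with anything from 0% and 12% to 12% and 0% at the two doses. That range, and the contrast between 4/20 and 4/15, rest on assumed counts. The second example was chosen for contrast and does not say why five subjects did not escalate when none had hypotension at 45 mg.

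**What to change.** Amend section 2.15.2 (Safety Analysis) as follows:

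1. Within Day 1, tabulate AEs by the most recent agent given before onset: baseline, inhaled NO, 45 mg, 90 mg. State the time after the last dose from which an event counts as post-treatment. Inhaled NO needs its own category because it comes before nitrite and would otherwise be merged with untreated baseline.
2. Use as denominator the number of subjects who received the agent or dose in question.
3. Add counts of Table 1 Moderate and Severe DLTs by dose, with exact 95% intervals.
4. State that 90 mg rates include any carry-over from 45 mg and exclude subjects stopped after 45 mg, so the two rates are descriptive and not a clean dose comparison.
5. Replace severe with serious in the expansion of SAE.

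No dose, visit or clinical rule changes. The cost is one or two extra tables, with small counts and wide intervals. The sponsor should confirm that the worksheets record AE onset time. If they do not, the dose period under which the AE was assessed (section 2.10.2) can be used for the allocation. The change is best made before the safety data are summarised.

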#### Pharmacokinetic Analysis

PK endpoints will be summarized using descriptive statistics. The actual sampling times will be used in calculating PK parameters using non-compartmental methods. The PK endpoints namely, AUC, Incremental recovery,  $t_{1/2}$ , CI, AUClast, Cmax will be analyzed using a multiplicative linear mixed effect models.

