#### AIR001 Dose 1 45 mg Nebulized

- Non-invasive blood pressure measurement
- PK, cGMP and platelet mitochondrial samples (approx. 15 minutes after nebulization)
- RA, PA, PCWP, CO/CI (approx. 15, 30, 45, 60 minutes after nebulization)
- AE assessment
- Methemoglobin (MetHgb) measurements (approx. 5, 15, 30, 60 minutes after nebulization)

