## 2.11. SCHEDULE OF ACTIVITIES (STUDY ASSESSMENT TABLE)

The table below summarizes the protocol procedures that will be performed at screening, during the study treatment, and at follow-up.

Study Phase	Screening	Pre-Treatment	Treatment				Post-Treatment Follow-Up Monitoring	
Visit Type	Outpatient Clinic	Outpatient Cath Lab				Phone Assessment	Outpatient Clinic	
Days on Intervention	Day 0	Day 1				Day 3	Day 30	
Study Procedures		Baseline	Dose 1	Dose 2	Final Measurement			
Informed Consent	X							
Medical History and Demographics	X							
I/E Criteria	X							
Physical Exam	X	X					X	
Vital Signs	X	X					X	
Oxygen Saturation	X	X	X	X	X		X	
Laboratory Tests***	X	X					X	
Urine Pregnancy Test Δ	X	X						
Non-invasive blood pressure measurement		X	X	X				
Right Heart Catheterization (RHC): RA, RV, PA, PCWP, CO/CI (RV measurements at baseline, pre-dose and 60minute interval post last dose AIR001)		X	X	X	X			
Micromanometry		X			X			
Echocardiogram		X			X			
Inhaled NO at 40 ppm if PCWP < 25		X						
PK Sampling*		X	X	X				
metHgb Level§		X	X	X	X			
Plasma cGMP		X	X	X				
Platelet Mitochondrial Analysis		X	X	X				
AE Assessment	X	X	X	X	X	X	X	
Interval History Assessment						X		

Δ Urine pregnancy test will be performed only on female of childbearing potential.

\*\*\* Clinical laboratory tests may be repeated on study visit 1 if screen lab results deemed clinically significant and warrant repeat testing or inadvertently not collected at screen visit.

\* PK Sampling for Nitrite: Blood samples will be obtained at pre-dose and at the end of nebulization at the presumed peak nitrite concentration for each tolerated dosage time points; 15 minutes post inhalation.

§ Methemoglobin (metHgb) levels: will be measured at the following time points: pre-dose, 5, 15, 30 and 60 minutes each dose of AIR001 and at 120 minutes post last dose of AIR001.

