### **2.12.2. Pulmonary Capillary Wedge Pressure**

Pulmonary capillary wedge pressure (PCWP) provides an indirect estimate of left atrial pressure (LAP). PCWP is measured by the balloon-tipped, multi-lumen catheter (Swan-Ganz catheter) while it is in a branch of the pulmonary artery. Just behind the tip of the catheter is a small balloon that can be inflated with air (~1 cc). The catheter has one opening (port) at the tip (distal to the balloon) and a second port several centimeters proximal to the balloon. These ports are connected to pressure transducers. When properly positioned in a branch of the pulmonary artery, the distal port measures pulmonary artery pressure and the proximal port measures right atrial pressure. The balloon is then inflated, which occludes the branch of the pulmonary artery. When this occurs, the pressure in the distal port rapidly falls, and after several seconds, reaches a stable lower value that is very similar to left atrial pressure (normally about 8-10 mmHg). The balloon is then deflated and pulmonary artery pressure can again be recorded. The same catheter can be used to measure cardiac output. Blood samples will be withdrawn from the tip of the wedged catheter at baseline (pre-dose), and at 15 minutes after each dose of inhaled nitrite (45 mg dose and 90mg).

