#### **2.12.5. Pharmacokinetic (PK) Studies**

Pharmacokinetic studies will be performed on all subjects enrolled to measure the concentration of inhaled nitrite and its metabolites in blood. The evaluation of the relationship between dosage and blood concentrations, and the relationship between blood concentrations and pharmacologic effects will provide valuable mechanistic information about the effects of inhaled nitrite on cardiopulmonary hemodynamics in Subjects with Pulmonary Hypertension.

To determine the pharmacokinetic profiles of the inhaled nitrite, blood samples will be collected at pre-nitrite dosing and at the end of nebulization at the presumed peak nitrite concentration for each tolerated dosage time points; approximately 15 minutes post inhalation. Vital signs, blood pressure and pulse oximetry will be measured and monitored closely at each time points. Samples will be immediately centrifuged and frozen at -20°C until the time of analysis.

PK samples will be accurately recorded for the collection time. Covariate information, e.g., age, body weight, height, disease type, concomitant medications, laboratory values, etc., will be obtained at the study visit. This is expected to yield an information-rich data set through dense sampling, enabling better characterization of the PK relationship of inhaled nitrite in subjects with PAH.

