### **2.12.8. Specimen collection and management**

#### Specimen Collection / Documentation

At each sampling time, one mL of blood will be withdrawn and discarded to assure that the solution used to maintain catheter patency does not dilute the sample. Blood samples will be accurately recorded for the actual sample collection time. Each research PK sample will be labeled with subject's unique identifier, sample date, scheduled sample collection time, and actual sample collection time. Covariate information, e.g., age, body weight, height, disease type, concomitant medications, laboratory values, etc., will be obtained at each time point. This is expected to yield an information-rich data set through dense sampling, enabling better characterization of the biomarkers in this patient population.

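### Half-life, and AUC if it is extrapolated, cannot be estimated by non-compartmental methods from one nitrite sample after each dose

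*Combined protocol and SAP*

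**What the plan says.** The analysis text in section 2.15.2 (Pharmacokinetic Analysis) reads "The actual sampling times will be used in calculating PK parameters using non-compartmental methods". It names AUC, incremental recovery, half-life, an item printed as CI, AUClast and Cmax, all to go into a multiplicative linear mixed model. The General Approach paragraph of the same section assigns "the PK endpoints (eg: AUC) for all doses of nitrite" to repeated measures ANOVA.

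The sampling text is consistent across the protocol:

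- Section 2.10.2 has one pre-dose draw. The dose 1 and dose 2 lists then each carry a single line: "PK, cGMP and platelet mitochondrial samples (approx. 15 minutes after nebulization".
- The footnote to the schedule in section 2.11 says "Blood samples will be obtained at pre-dose and at the end of nebulization at the presumed peak nitrite concentration", and gives 15 minutes post inhalation as the time.
- Section 2.12.2 takes wedge-catheter blood at baseline and "at 15 minutes after each dose of inhaled nitrite".
- Section 2.12.5 places the post-dose draw "at the presumed peak nitrite concentration for each tolerated dosage time points; approximately 15 minutes post inhalation".

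Section 2.12.5 nonetheless says of these data: "This is expected to yield an information-rich data set through dense sampling". Section 2.12.8 repeats the claim for the biomarkers: "information-rich data set through dense sampling, enabling better characterization of the biomarkers in this patient population".

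**The concern.** The list of PK parameters suits a trial that follows the concentration curve through its decline. This trial takes one reading per dose, near a peak that is presumed rather than observed. Three things follow.

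- Part of the promised analysis cannot be carried out.
- An AUC reported under the General Approach paragraph would look like a measure of exposure while carrying nothing beyond one concentration per dose.
- The reading after 90 mg includes whatever remains of the 45 mg dose. If the two readings were treated as two separate doses, a dose-proportional drug could look more than proportional.

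**Working it through.** The plan gives no sample size, precision or assumed half-life for the PK analysis, so there is no figure to reproduce. The check is a count of samples followed by algebra.

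**1. Samples per subject** (sections 2.10.2, 2.11, 2.12.2, 2.12.5). 1 pre-dose + 1 after 45 mg + 1 after 90 mg = 3 at most, or 2 if dosing stops after 45 mg. Mixed venous and wedge samples add sites, not times.

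**2. Terminal slope.** Half-life = ln 2 / λ, where λ is the slope of log concentration over declining samples. A straight line has two parameters, so m samples leave m − 2 residual degrees of freedom: −1 for m = 1 (not estimable), 0 for m = 2 (a line with no check of fit), 1 for m = 3. Here m = 1 for each dose. The dose 2 sample does not lie on the decline from dose 1, because it follows a new and larger dose.

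Extrapolated AUC = AUClast + C/λ, so it fails for the same reason. To illustrate, set the dose 1 reading to 1 above baseline, with a 10-minute nebulization and the pre-dose draw at its start. AUClast = 0.5 × 1 × (10 + 15) = 12.5. The extrapolated part is half-life / ln 2, which is 14.4 for an assumed 10 minutes and 173.1 for 120 minutes. The total is 26.9 or 185.6, a 6.9-fold range from identical data.

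**3. AUClast.** With two points, dose 1 AUClast above baseline = C1 × D/2, where D is the actual time between the draws. D = L + T + 15, with T = 10–15 minutes of nebulization (section 2.7.4) and L the lag from pre-dose draw to start of nebulization, for which section 2.10.2 sets no value. If L = 0 the multiplier is 12.5–15 minutes; with an assumed L of 10 it is 17.5–20. The multiplier varies with the timing of the draws, not with drug disposition. For dose 2 there is no sample at the start of the interval, so AUClast also needs a starting value that the plan does not state.

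**4. Carry-over into the dose 2 reading.** Section 2.10.2 requires a hemodynamic reading 60 minutes after dose 1 nebulization ends, and the Synopsis puts dose 2 about 60 minutes after dose 1. Counting from the end of dose 1, sample 1 is at 15 minutes and sample 2 at 60 + T + 15, so the gap is 60 + T = 70–75 minutes. Assume exact dose proportionality (section 1.3.5 reports it for peak and AUC, in normal volunteers) and one-phase decline. Then:

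- ratio of the 90 mg to the 45 mg reading, r = 2 + 2^(−gap/half-life)
- residual share of the second reading = 2^(−gap/half-life) / r

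| Assumed half-life (min) | r, gap 70 | Residual | r, gap 75 | Residual |
|---|---|---|---|---|
| 15 | 2.04 | 1.9% | 2.03 | 1.5% |
| 30 | 2.20 | 9.0% | 2.18 | 8.1% |
| 60 | 2.45 | 18.2% | 2.42 | 17.4% |
| 90 | 2.58 | 22.6% | 2.56 | 21.9% |

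If the Synopsis interval were counted from the start of dose 1, the gap would be 60 minutes and the share larger: at a 30-minute half-life, 0.25/2.25 = 11.1%.

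**The case against.** The strongest reply is that little hangs on this. Neither list of secondary endpoints (Synopsis, section 2.13.2) contains half-life or AUC; both use changes in concentration, which the samples support. Several passages make PK sampling optional. No dose-proportionality test is planned. All of that stands, and it keeps the point small. It does not make the parameters listed in section 2.15.2 estimable.

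One could read end of nebulization and 15 minutes post inhalation as two draws. The dose lists in section 2.10.2 and section 2.12.2 show only the 15-minute draw, and two points would still leave no check of fit. A population model with outside information could estimate more, but the plan specifies non-compartmental methods and names no such source.

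A reader might infer more than the documents support in four ways:

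- *That the plan definitely promises AUC to infinity.* It never says so; listing AUC apart from AUClast only suggests it. Half-life is the firm part.
- *That no AUC can be computed, or that the 90/45 mg AUC ratio would be grossly inflated.* AUClast is computable. A very large ratio appears only if a 70–75 minute window for dose 2 is set against 25–30 minutes for dose 1; it mostly reflects unequal windows, and no section proposes that calculation.
- *That carry-over is known to be material.* Its size rests wholly on an assumed half-life and is negligible at 15 minutes.
- *That Aim 4 fails.* It concerns measures of drug exposure and cGMP, and the relation between the 15-minute nitrite concentration and cGMP can still be studied. Aim 4 is narrowed; it is neither lost nor untouched.

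**Conclusion.** The point holds. Half-life is not estimable in any subject on the planned samples, and the same is true of AUC if it means extrapolated AUC. This follows from the schedule alone. Clearance would fail too if that is what the item printed as CI means, but the conclusion does not depend on it. AUClast adds no exposure information to the single concentration, and the 15-minute value is a presumed rather than an observed Cmax.

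Carry-over from 45 mg cannot be separated from the 90 mg reading. That is certain; its size is not, and the percentages above illustrate it under dose proportionality and one-phase decline. Describing at most three time points as dense sampling is inaccurate.

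The primary PVR analysis and the concentration endpoints stand. This should be corrected, but it sits at the lower end of importance.

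**What to change.** - **Section 2.15.2, Pharmacokinetic Analysis:** drop half-life, extrapolated AUC and any other listed parameter that needs a terminal slope. Do not present AUClast as exposure or the 15-minute value as an observed Cmax. Define the PK endpoint as plasma nitrite about 15 minutes after each dose relative to pre-dose, analysed on the log scale with the multiplicative mixed model already named there, and relate it to cGMP drawn at the same time.
- **Section 2.15.2, General Approach:** replace the AUC example with a reference to the Pharmacokinetic Analysis paragraph, so that one model applies to the PK endpoint.
- **Dose comparison:** describe it as cumulative, that is 45 mg, then 45 mg followed by 90 mg.
- **Sections 2.12.5 and 2.12.8:** remove the statement that sampling is dense.

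This changes wording only, with no added draws and no change to procedures. It also brings the analysis into line with the concentration endpoints in the Synopsis and section 2.13.2. The cost is that the trial will not report a half-life or total exposure in this population. Keeping those parameters would require further timed samples during the decline after a dose, which the current schedule does not contain.
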